7.6.2 Expression of CD30 on neoplastic mast cells

The burden of CD30+ neoplastic mast cells will be determined by immunophenotyping and/or immunohistochemistry and will be compared between pre- and post-SGN-35 treatment samples. Evaluation will be undertaken by central pathology review by [name] at University of New Mexico. Reduction of mast cell burden will also be recorded pre-and post SGN-35 therapy primarily by evaluation of peripheral blood (if mast cell leukemia) and bone marrow aspirate and core biopsy. Change of serum tryptase levels from baseline at the respective assessments will be evaluated as a surrogate marker for histopathologic response.

7.6.3 Myeloproliferative Neoplasm Symptom Assessment Form (MPNSAF) modified for Mast Cell Symptoms

Total symptom score and QOL will be assessed by a modified version of the MPNSAF (modified for mast cell symptoms) by recording mean and median scores with ranges will be recorded pre- and post-treatment with SGN-35 (Appendix F).

7.6.4 Duration of Response (DoR) and Time to Response (TTR)

The duration of (confirmed) overall response (DoR) is defined as the time from the start of the first confirmed response until the date of the first documented and confirmed disease progression or death due to ASM or MCL. The Kaplan-Meier product-limit method will be used to summarize the response duration. If a patient did not progress or die due to ASM or MCL at the time of the analyses, DoR will be censored at the date of the last adequate response assessment.

Time to response (TTR) is defined as the time from the date of start of treatment to the date of first confirmed response. Time to response will be censored at the date of the last adequate response assessment in patients did not progress or die due to any cause and at maximum follow-up date (ie, date of first patient first visit (FPFV) to date of last patient last visit (LPLV) used for the analysis) in patients who progressed or died due to any cause. Kaplan-Meier product-limit estimates will be used to summarize the time to response.

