In approximately 30% of SM patients, an AHNMD (myeloid malignancy) is diagnosed. The subvariant categories of AHNMD include SM-AML (acute myeloid leukemia), SM-MDS (myelodysplastic syndrome), SM-MDS/MPN (MDS/myeloproliferative neoplasm, eg, chronic myelomonocytic leukemia), and SM-HES or SM-CEL (hypereosinophilic syndrome or chronic eosinophilic leukemia). Generally, separate treatment plans for the SM and the AHNMD should be established for these patients. However, the SM and AHNMD may share a common pathophysiologic link, and particular treatments may be useful for both the SM and myeloid malignancy. Although the intent of SM-directed therapy is to target neoplastic mast cells, it may not always be possible to identify whether organ damage is due to the SM or AHNMD component or both. Patients with CEL-associated with the FIPL1-PDGFR α fusion gene may exhibit increased mast cells in the bone marrow but are not classified by the WHO as having systemic mastocytosis. It is recommended that such patients be treated with imatinib ([Valent et al. 2007](#)) and would not be considered eligible for this protocol.

The most important growth factor for mast cells seems to be stem cell factor (SCF) also termed mast cell growth factor or KIT ligand. SCF induces the development of mast cells from their uncommitted CD34+ progenitors. The effects of SCF on mast cells and mast cell

progenitors are mediated through KIT, a tyrosine kinase receptor (for SCF) encoded by the KIT proto-oncogene. SCF and SCF-dependent activation of KIT are essential to the development and differentiation of mast cells. “Gain-of-function mutations” in the kinase domain of *KIT* are associated with enhanced growth of mast cells and their progenitors. Such mutations (eg, D816V) are frequently detected in patients with SM ([Valent et al. 2005](#)).

Specific gene defects are well recognized as the oncogenic factors in SM. The *KIT* D816V mutation expressed in neoplastic mast cells is by far the most common and is found in all variants of SM. Highly sensitive methods have detected that >90% of patients with SM carry the D816V *KIT* mutation. Several other *KIT* gene defects have been identified in patients with mast cell disease, but each are likely to be present in less than 5% of diagnosed patients ([Sotlar et al. 2003](#), [Garcia-Montero et al. 2006](#), [Valent et al. 2005](#)).

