2.3.2 Secondary Efficacy Endpoints

- Immunohistochemical expression of CD30 on neoplastic mast cells in core biopsy samples or by flow before SGN-35 treatment and after 4 and 8 cycles of therapy
- Total symptom score and QOL score using a modified Myeloproliferative Neoplasm Symptom Assessment Form (MPN-SAF)
- Duration of response (DoR) is defined as the time from first onset of confirmed response to the date of first documented and confirmed progression or death due to ASM/MCL. Time to response (TTR) is defined as the time from start of treatment until the date of onset of a confirmed response
- Progression-free survival (PFS) is defined as the time from start of treatment to the date of the first documented and confirmed progression or death or institution of new therapy

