4.7.1 Rules for deriving the variable confirmed overall response

The confirmation response is the next valid consecutive response at least 84 days (12 weeks) from initial response. The time of response is the actual date of response, not the end of cycle which includes the response.

In patients whose response commences in later cycles before the end of cycle 8 (eg, during cycle 6, 7, or 8), the duration of response will be assessed by ongoing laboratory studies and ongoing visits, performed every 6 weeks. Patients who exhibit a response during cycles 1-8 (or during cycles 9-16), but subsequently demonstrate loss of response before cycle 8 is completed (or before cycle 16 is completed for patients being re-treated), such individuals will not be re-treated. Retreatment after cycles 1-8 is only applicable to patients who exhibit an ongoing response at the time of completion of cycle 8.

In case report forms/study e-CRFs, the confirmed response will be denoted by a subscript 'c', whereas initial responses or unconfirmed responses (eg, responses not yet lasting 12 weeks) will display the subscript 'uc'. For example, if a Major response is confirmed at 12 weeks (Table 3 below, column 3), it will be denoted as 'Major Response_c' or 'MR_c'; whereas an initial Major Response will be denoted as 'Major Response_{uc}' or 'MR_{uc}'.

Table 3 Acceptable combinations for initial and confirmed response

Initial Response	Response at 12 weeks	Confirmed response level
Major _{uc}	Major _{uc}	Major _c
Major _{uc}	Partial _{uc}	Partial _c
Partial _{uc}	Partial _{uc}	Partial _c
Partial _{uc}	Major _{uc}	Partial _c
Cl _{uc}		Cl _c
Cl _{uc}	Cl _{uc}	Cl _c
Cl _{uc}		Cl _c
Partial _{uc}	Major _{uc}	Cl _c
Major _{uc}	Partial _{uc}	Cl _c
	Cl _{uc}	
	Cl _{uc}	

CI: "Clinical Improvement" per international response criteria

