(2) Development of at least 10-cm palpable symptomatic splenomegaly for a baseline spleen size of not palpable or ≤ 5 cm, OR if baseline symptomatic splenomegaly is > 5 cm, a $> 50\%$ worsening and development of at least 10 cm of palpable symptomatic splenomegaly compared with the baseline value.¶

Loss of response (LOR)

Loss of a documented CR, PR, or CI that must be for ≥ 8 wk. Downgrading of CR to PR or PR to CI is considered as such but is not considered as loss of response unless CI is also lost for a minimum of 8 wk. The baseline value for LOR is the pretreatment measurement(s) and not the nadir values during response.

Guidelines for adjudicating response are as follows: (1) Only disease-related \geq grade 2 organ damage is evaluable as a primary endpoint in clinical trials. (2) Response adjudications of CR, PR, SD, PD, and LOR should only be applied to these \geq grade 2 organ damage findings in the context of trials. (3) Disease status at the time of patient removal from the study singularly relates to the updated status of initial \geq grade 2 organ damage finding(s). (4) Exclusion of drug-related toxicity and/or other clinical issues (eg, gastrointestinal tract bleeding in the case of worsening anemia/transfusion-dependence) should be undertaken before assigning the designation PD or LOR in a patient with worsening of baseline \geq grade 2 organ damage.

*Responses that are not maintained or confirmed for a period of at least 12 wk do not fulfill criteria for CR, PR, or CI; however, both maintained and unmaintained (< 12 -wk duration) responses in organ damage should be recorded to determine median duration of response.

†Only valid as a response criterion if the pretreatment serum tryptase level is ≥ 40 ng/mL.

‡Biopsy of organ(s) in addition to the BM to evaluate for SM-related organ damage may be considered.

§Preservation of at least one CI finding permits a patient to maintain the response of 'CI' if 1 or more CI findings are lost but none meet criteria for progressive disease (PD). However, if 1 or more of the CI findings become PD, then the CI finding assignment is lost and the patient meets criteria for PD. The baseline value for evaluating PD is the pretreatment measurement(s). The PD findings must be considered related to the underlying disease and not to other clinical factors. Progression of an underlying chronic myeloid neoplasm to AML is also considered PD in the setting of clinical trials.

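### Duration of response leaves out responses under 12 weeks, censors deaths from other causes and ignores loss of response, so it will overstate the time patients spend in response

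*Combined protocol and SAP*

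**What the plan says.** Section 2.3.2 defines DoR as the "time from first onset of confirmed response to the date of first documented and confirmed progression or death due to ASM/MCL". Section 7.6.4 repeats this as "the time from the start of the first confirmed response until the date of the first documented and confirmed disease progression", with fatal ASM or MCL as the only other ending, and adds the censoring rule: "If a patient did not progress or die due to ASM or MCL at the time of the analyses, DoR will be censored". The censoring date is that of the last adequate response assessment. Kaplan-Meier is the stated method.

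Section 4.7.1 says what confirmed means: "The confirmation response is the next valid consecutive response at least 84 days (12 weeks) from initial response". It dates a response to the day it occurred, and has unconfirmed responses marked with a uc subscript on the CRF.

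The starred footnote to the response criteria in Appendix G says that responses not maintained for 12 weeks are not CR, PR or CI. It then says that maintained and unmaintained "responses in organ damage should be recorded to determine median duration of response". Appendix G also defines LOR as a category separate from progressive disease (PD).

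PFS in Section 7.6.5 ends at confirmed progression, death without restriction of cause, or new therapy. Section 3.2 allows a responder who meets LOR to be re-staged and re-treated.

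**The concern.** Section 1.1 notes that responses to interferon or cladribine are mostly partial and short-lived, so readers will look at DoR to see whether this drug does better. They will take it as the time patients spend in response. As defined, it is something else.

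- Responses that fade before 12 weeks are left out, and Section 7 plans no other use of them.
- A responder who dies of the AHNMD, of toxicity or of an unrelated cause without confirmed progression is treated like a patient whose response is continuing but not yet fully observed.
- A responder who meets LOR without meeting PD has no DoR event. That patient can be re-treated and still count as in response.

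All three push the reported duration upward. With at most 26 patients and only some of them responding, how one or two patients are handled can move the median.

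**Working it through.** **Plan's own figures.** The documents state no DoR figure. Their only stated operating characteristics are those of the Simon design in Section 7.8, which does not use DoR. Exact binomial calculation (continue on at least 2 of 11, succeed on at least 5 of 26) gives alpha 0.0865, power 0.8516, and early stopping 0.6974 at a 10% rate and 0.1130 at 30%. These match the stated 8.7%, 85%, 70% and 11%.

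**Which endings count, by section.**

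| Ending | DoR (2.3.2, 7.6.4) | PFS (7.6.5) |
|---|---|---|
| Confirmed progression | event | event |
| Death due to ASM or MCL | event | event |
| Death from another cause | censored | event |
| LOR without PD | not an event | not an event |

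Omitting LOR is natural for PFS, which does not measure time in response. For DoR it leaves out the most direct way a response ends.

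**The 12-week floor.** A response enters only if it is still present at day 84 or later, and its clock starts at onset. No included patient can have an event before day 84, so the curve stays at 100% until then.

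**Illustrative size (assumptions, not document figures).** Let time from onset to the end of response, from any cause, be exponential with median *m* weeks. Let a share *s* of endings be deaths from causes other than ASM or MCL, occurring at a constant proportion of the hazard.

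- Share of responses reaching 12 weeks: 2^(−12/*m*).
- Median from onset among those reaching 12 weeks: 12 + *m*, because the exponential has no memory.
- Kaplan-Meier median when other-cause deaths are censored: the event hazard falls to (1 − *s*) ln 2/*m*, so the median is *m*/(1 − *s*).
- Both together: 12 + *m*/(1 − *s*).

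| *m* (weeks) | Share reaching 12 weeks | Floor alone | Both, *s* = 20% | Both, *s* = 30% |
|---|---|---|---|---|
| 12 | 0.500 | 24 | 27.0 | 29.1 |
| 24 | 0.707 | 36 | 42.0 | 46.3 |
| 48 | 0.841 | 60 | 72.0 | 80.6 |

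For *m* = 24 the death rule alone gives 24/0.9 = 26.7, 24/0.8 = 30.0 and 24/0.7 = 34.3 weeks at *s* = 10%, 20% and 30%. A simulation of 200,000 durations per setting agrees with the combined formula to within 0.4 weeks.

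**Loss of response.** No figure is computed. After LOR the clock runs on to a later PD, an ASM or MCL death, or the last adequate assessment. The documents give nothing on how long that interval would be. The direction is again upward.

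**The case against.** The best defence is that 7.6.4 labels its quantity as the duration of confirmed overall response. Appendix G itself denies the name CR, PR or CI to anything under 12 weeks, so restricting DoR to confirmed responses is coherent. Short responses are not hidden either, since they count as non-response in the primary endpoint. This stands, and it is why confirmed-response DoR should be kept. It does not answer the second half of the same footnote, which asks for a median duration that includes unmaintained responses. The CRF captures them, but Section 7 never analyses them.

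It is also fair that DoR is secondary and descriptive, with no test or decision attached, and that PFS counts all deaths and survival is followed separately. That limits the consequence. It does not make the DoR rule right.

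Several stronger readings are tempting but not supported:

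- **The death rule contradicts Appendix G.** Appendix G does not say which deaths end a response. The mismatch is with PFS.
- **Only disease deaths end DoR.** Confirmed progression ends it too. The restriction concerns which deaths count.
- **The clock starts at week 12.** It starts at onset. The problem is which responses are selected.
- **Cause of death usually cannot be assigned.** Section 1.1 says only that "it may not always be possible to identify whether organ damage is due to the SM or AHNMD component or both", which concerns organ damage and is not a statement about frequency. It is reason for caution about attribution, no more.
- **Deaths from AML are widely missed.** Appendix G states that "Progression of an underlying chronic myeloid neoplasm to AML is also considered PD in the setting of clinical trials", and patients whose AHNMD needs immediate treatment are excluded. The gap is limited to AML deaths without documented, confirmed progression.

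**Conclusion.** The point holds in three parts. First, DoR has a built-in 12-week floor, and the duration measure that Appendix G calls for is not planned. Second, deaths from other causes are censored in DoR but are events in PFS. Third, LOR does not end a response.

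Each part lengthens DoR relative to the time patients are actually in response. The direction follows from the definitions. The size cannot be obtained from the documents. A reader might take the 12-week increase in the median as the bias of this trial, but it is a property of the exponential assumption. The illustration also treats any end of response as the ending, including losses that 7.6.4 does not count. The multiplier 1/(1 − *s*) rests on an assumed share of deaths and constant hazards.

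The weight is moderate: a secondary descriptive endpoint in 11 to at most 26 patients, on a question the protocol itself raises about existing treatments. The response rate and the Simon decision rules do not change.

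**What to change.** Amend Sections 2.3.2 and 7.6.4 together:

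1. Count LOR, PD and death from any cause as DoR events. Keep the current version, in which only ASM or MCL deaths count, as a sensitivity analysis.
2. Keep confirmed-response DoR, and state in the text and table title that it is conditional on at least 12 weeks of response.
3. Add the median duration over all documented organ-damage responses, maintained and unmaintained, using the uc records already on the CRF. Appendix G words LOR for a documented CR, PR or CI, so state how the end of an unconfirmed response is defined and dated. Without this, a short response that fades without PD has no end.

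The cost is a wording change and one more table from response data already collected. The downside is that the reported median will be less favourable.

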3.2 Discussion of design

Patients will receive open label SGN-35 at a starting dose of 1.8 mg/kg administered as a single IV infusion as on Day 1 of each 21-day cycle as an outpatient. Patients will be treated for eight 21-day cycles. The best response per international response criteria will be recorded by the end of cycle 8. Because responses must last at least 12 weeks, any clinical improvement (CI), partial response (PR), or CR response that commences by the end of cycle 8, and either persists or evolves into a higher quality response for at least 12 weeks will be counted as a response. Patients who demonstrate a response and subsequently meet criteria for loss of response (LOR) will be permitted to undergo re-staging and re-treatment with up to an additional 8 cycles of SGN-35.

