4.7.2 Additional aspects to disease evolution

The international consensus response criteria define both progressive disease and loss of response (see Appendix G).

A study of brentuximab vedotin (SGN-35) in CD30-positive systemic mastocytosis with or without an associated hematological clonal non-mast cell lineage disease (AHNMD)

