APPENDIX G Contd.:

APPENDIX G: WG-MRT-ECNM consensus response criteria for patients with ASM, MCL, and SM associated with a myeloid neoplasm

Complete remission (CR)*

Requires all 4 criteria and response duration must be ≥ 12 wk

No presence of compact neoplastic mast cell aggregates in the BM or other biopsied extracutaneous organ

Serum tryptase level < 20 ng/mL†

Peripheral blood count remission defined as ANC $\geq 1 \times 10^9/L$ with normal differential, Hb level ≥ 11 g/dL, and platelet count $\geq 100 \times 10^9/L$

Complete resolution of palpable hepatosplenomegaly and all biopsy-proven or suspected SM-related organ damage (CI findings)‡

Partial remission (PR)*

Requires all 3 criteria and response duration must be ≥ 12 wk, in the absence of both CR and progressive disease (PD)

Reduction by $\geq 50\%$ in neoplastic MCs in the marrow and/or other extracutaneous organ at biopsy demonstrating eligible SM-related organ damage

Reduction of serum tryptase level by $\geq 50\%$ †

Resolution of 1 or more biopsy-proven or suspected SM-related organ damage (CI finding(s)) ‡

Clinical improvement (CI)*

Response duration must be ≥ 12 wk

Requires 1 or more of the nonhematologic and/or hematologic response criteria to be fulfilled (see Table 3) in the absence of both CR/PR assignment or progressive disease (PD)

Stable disease (SD)

Not meeting criteria for CR, PR, CI, or PD

Progressive disease (PD)§

Requires at least 1 element of either criteria 1 or 2 and duration must be ≥ 8 wk

(1) For patients with baseline grade 2 nonhematologic organ damage: a) worsening by 1 grade, AND b) minimum 100% increase (doubling) of laboratory abnormality.

For patients with baseline \geq grade 2 albumin: (a) worsening by 1 grade, AND (b) decrease by ≥ 0.5 g/dL.

For patients with baseline \geq grade 3 nonhematologic organ damage: minimum 100% increase (doubling) of laboratory abnormality.

For patients with baseline \geq grade 2 transfusion-independent anemia or thrombocytopenia: New transfusion dependence of ≥ 4 units of RBCs or platelets at 8 wk.

For patients with baseline transfusion-dependent anemia or thrombocytopenia: $\geq 100\%$ increase in the average transfusion frequency for an 8-wk period compared with the 12-wk pretreatment period

For patients with baseline grade \geq grade 3 neutropenia: (a) $> 50\%$ decrease in neutrophil count, AND (b) absolute decrease of neutrophil count of $\geq 250/mm^3$, AND c) grade 4

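### Duration of response has no loss-of-response event, so time after a response has been lost can be counted as response

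*Combined protocol and SAP*

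**What the plan says.** DoR is defined twice. Section 2.3.2 gives it as "time from first onset of confirmed response to the date of first documented and confirmed progression or death due to ASM/MCL". Section 7.6.4 ends it in the same way, "until the date of the first documented and confirmed disease progression or death due to ASM or MCL", and adds the censoring rule: "If a patient did not progress or die due to ASM or MCL at the time of the analyses, DoR will be censored", the date being that of the last adequate response assessment. That term is not defined.

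Section 4.7.2 treats losing a response and progressing as two things: "The international consensus response criteria define both progressive disease and loss of response". In Appendix G, LOR is loss of a documented CR, PR or CI lasting at least 8 weeks, and "The baseline value for LOR is the pretreatment measurement(s) and not the nadir values during response". PD is also measured from pretreatment values.

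The protocol acts on LOR. Section 3.2 states: "Patients who demonstrate a response and subsequently meet criteria for loss of response (LOR) will be permitted to undergo re-staging and re-treatment", for up to 8 further cycles. Section 4.7.1 limits this to patients still in response when cycle 8 is completed. Section 4.6.1 takes patients off study at LOR after re-treatment. None of these sections links LOR to DoR.

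**The concern.** DoR is a named secondary endpoint and the only one that describes how long responses last. A responder who falls back to the pretreatment state has lost the response but need not have PD. Under the written rule that patient's clock keeps running, through re-treatment if it is given, until PD, disease death or censoring. A patient who leaves without PD is censored although the failure is known, which makes the censoring informative. Either way the Kaplan-Meier estimate overstates durability. Some failures are PD from the start (transformation to AML, or a CI finding that itself becomes PD). For those the written rule is correct, so the size of the error depends on the mix.

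**Working it through.** The plan states no figure for DoR, so there is none to reproduce.

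**1. Can LOR occur without PD?** Two findings in Appendix G, assuming no other CI finding is preserved:

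- *Spleen palpable 8 cm at baseline.* CI needs a reduction of at least 50%: 8 × 0.5 = 4 cm or less, without symptoms. PD by palpation needs more than 50% worsening "and development of at least 10 cm of palpable symptomatic splenomegaly compared with the baseline value": 8 × 1.5 = 12, so more than 12 cm. Regrowth to between 4 and 12 cm for at least 8 weeks ends this CI without PD by palpation. If 3D volume is used, PD starts at +25% volume. A spleen that has only returned to its baseline size is PD on neither measure.
- *Transfusion-independent anemia.* CI is a hemoglobin gain of at least 2 g/dL. PD for patients with baseline "grade 2 transfusion-independent anemia or thrombocytopenia: New transfusion dependence of" at least 4 units at 8 weeks. Hemoglobin back at baseline for 8 weeks is LOR and not PD.

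**2. Time added, from the documents alone.** LOR needs at least 8 weeks of loss. Cycles 9-16 last 8 × 21 days = 24 weeks. From first loss to completion of cycle 16 is at least 8 + 24 = 32 weeks (224 / 30.44 = 7.4 months). Counting instead from declared LOR, with the full 21-day re-staging window, gives 3 + 24 = 27 weeks. The two figures differ only in where they start and in whether re-staging time is included.

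**3. Effect on the median (assumed rates).** No failure in the first 12 weeks (2.76 months), then a constant hazard λ giving a true median of 6.0 months: 6.0 − 2.76 = 3.24, so λ = ln 2 / 3.24 = 0.214 per month. A share p of failures is direct PD. The rest are LOR, followed by PD after an exponential gap with median g and rate μ = ln 2 / g. At t = 2.76 + u the plan's curve is

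S = p·e^(−λu) + (1 − p)·(λe^(−μu) − μe^(−λu)) / (λ − μ).

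For p = 0.5 and g = 6 (μ = 0.1155), u = 6.34 gives 0.5 × 0.258 + 0.5 × 0.742 = 0.50, so the median is 2.76 + 6.34 = 9.1 months. A simulation with independent follow-up of 12 to 30 months gives the same medians.

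| Direct PD share p | g = 3 months | g = 6 months | g = 12 months |
|---|---|---|---|
| 0 | 10.3 | 13.7 | 19.9 |
| 0.25 | 9.2 | 11.4 | 15.2 |
| 0.50 | 8.0 | 9.1 | 10.5 |
| 0.75 | 6.9 | 7.2 | 7.5 |
| 0.90 | 6.3 | 6.4 | 6.5 |

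With LOR counted as an event the median is 6.0 months throughout.

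**4. The other reading of the censoring rule.** Suppose the last adequate assessment means the last one still in response, and every LOR patient is censored there with no later PD recorded. The event hazard falls to pλ and the median becomes 2.76 + 3.24/p. That is 7.1, 9.2 and 15.7 months for p = 0.75, 0.50 and 0.25.

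**5. Deaths from other causes.** If a share s of end-of-response events is non-ASM/MCL death and is censored, the median is 2.76 + 3.24/(1 − s): 6.4, 6.8 and 7.4 months for assumed s of 0.1, 0.2 and 0.3.

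**The case against.** - **The 32 weeks are conditional.** They require response at the end of cycle 8, later LOR, all 8 re-treatment cycles and no PD, and they require the last adequate assessment to include visits after the loss. This stands as a limit on the figure. It does not rescue the rule: response assessments are scheduled through re-treatment, so the inclusive reading is the natural one, and step 4 shows that the narrow reading also biases the median upward.
- **The larger medians may need follow-up that the plan does not provide**, because assessment stops about 30 days after end of treatment in non-responders and at LOR after re-treatment. That turns some later PD into censoring, and the failure still goes uncounted. Allowing for removal from study after re-treatment leaves the medians essentially unchanged.
- **Few responders.** At a 30% response rate, 11 or 26 patients give about 3 or 8 responders. Even with LOR counted, the median in step 3 would vary from roughly 3 to 14 months with 3 responders and from 3.6 to 9.3 with 8. This is fair: sampling noise exceeds many of the shifts shown. But the bias runs one way, and the estimate would carry the wrong label.
- **3D volumes are scheduled**, which narrows the spleen gap. True, but return to baseline remains outside PD, and the anemia example is untouched.
- **Appendix G asks for maintained and unmaintained responses to be recorded** for the median duration. This helps the data exist; it adds no LOR event to Section 7.6.4.
- **Disease-specific death is an explicit choice.** Agreed. It is separable from the LOR point.

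**Conclusion.** The concern holds. Both definitions omit LOR, and Appendix G makes LOR without PD possible, so what is labeled duration of response is time to progression or disease death among responders. For each patient followed to an event it is never shorter than the true duration, and it is longer whenever LOR precedes PD. Without PD, the failure is either counted as continued response or censored informatively.

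The size cannot be fixed from the documents. It is negligible if nearly all failures are direct PD (0.3 to 0.5 months on a 6.0-month median at 90%), 2.0 to 4.5 months at 50%, and larger if most failures pass through LOR. These figures rest on the assumed hazards, gaps and follow-up in step 3. The primary endpoint and the Simon rules (2 of 11, 5 of 26) do not use DoR and are unaffected. It should be corrected before DoR is analyzed.

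**What to change.** In Sections 2.3.2 and 7.6.4:

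- Define DoR as the time from onset of the first confirmed response to the earliest of LOR (Appendix G), PD or death.
- Date LOR at the first scheduled response assessment showing a loss that then lasts at least 8 weeks, including LOR before the end of cycle 8. Dating it at the confirming visit would add 9 weeks on the 3-week cycle grid and 12 weeks on the 6-week or 12-week follow-up grid.
- Censor at the last adequate response assessment only if none of these events has occurred, and define that term.
- Stop the first-response clock at LOR, before re-treatment, and report the duration of any re-treatment response separately.
- Count death from any cause, as PFS already does in Section 7.6.5, or show it as a sensitivity analysis.

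The present definition can be kept under the label of time to progression in responders.

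The cost is wording only. Response assessments are already scheduled each cycle from cycle 2 and every 6, then every 12, weeks in follow-up, so no visit is added. The reported DoR will be shorter.
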